#### 8.1.3 Treatment with hormones or other chemotherapeutic agents may not be administered except for steroids given for adrenal failure (steroid supplementation should be at physiologic dosing or as described in [section 8.1.10](#)); hormones administered for non-disease-related conditions (e.g., insulin for diabetes); and intermittent use of dexamethasone as an antiemetic in solid tumor protocols.

#### 8.1.4 Antiemetics may be used at the discretion of the attending physician.

#### 8.1.5 Diarrhea: Please see Section [8.1.10](#) for further description of immune mediated colitis. All therapies for diarrhea are allowed on this protocol at the discretion of the treating investigator.

#### 8.1.6 Radiation therapy

Patients who require radiation therapy during protocol treatment will be removed from protocol therapy due to disease progression.

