## 11.0 MEASUREMENT OF EFFECT

Response and progression as primary endpoints will be evaluated in this study using the new international criteria proposed by the revised Response Evaluation Criteria in Solid Tumors (RECIST) guidelines (version 1.1).[47] Changes in the largest diameter (unidimensional measurement) of the tumor lesions and the short axis measurements in the case of lymph nodes are used in the RECIST guideline.

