#### 11.4.3.2 Evaluation of Target Lesions

**Important: Refer to [Section 11.1](#) for a full description of the correct baseline scan to use due to the retreatment after PD during treatment in the 1st 12 weeks, as well as baseline scan to be used for crossover treatment.**

- **Complete Response (CR):** All of the following must be true:
  - a. Disappearance of all target lesions.
  - b. Each target lymph node must have reduction in short axis to < 1.0 cm.
- **Partial Response (PR):** At least a 30% decrease in PBSD (sum of the longest diameter for all target lesions plus the sum of the short axis of all the target lymph nodes at current evaluation) taking as reference the BSD (see [Section 11.4.1](#)).
- **Progression (PD):** At least one of the following must be true:
  - a. At least one new malignant lesion, which also includes any lymph node that was normal at baseline (< 1.0 cm short axis) and increased to  $\geq$  1.0 cm short axis during follow-up.
  - b. At least a 20% increase in PBSD (sum of the longest diameter for all target lesions plus the sum of the short axis of all the target lymph nodes at current evaluation) taking as reference the MSD ([Section 11.4.1](#)). In addition, the PBSD must also demonstrate an absolute increase of at least 0.5 cm from the MSD.
  - c. See [Section 11.3.2](#) for details in regards to the requirements for PD via FDG-PET imaging.
- **Stable Disease (SD):** Neither sufficient shrinkage to qualify for PR, nor sufficient increase to qualify for PD taking as reference the MSD.

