#### 11.4.3.3 Evaluation of Non-Target Lesions & Non-target Lymph Nodes

**Important: Refer to [Section 11.1](#) for a full description of the correct baseline scan to use due to the retreatment after PD during treatment in the 1st 12 weeks, as well as baseline scan to be used for crossover treatment.**

- **Complete Response (CR):** All of the following must be true:
  - a. Disappearance of all non-target lesions.
  - b. Each non-target lymph node must have a reduction in short axis to <1.0 cm.
- **Non-CR/Non-PD:** Persistence of one or more non-target lesions or non-target lymph nodes.
- **Progression (PD):** At least one of the following must be true:
  - a. At least one new malignant lesion, which also includes any lymph node that was normal at baseline (< 1.0 cm short axis) and increased to  $\geq$  1.0 cm short axis during follow-up.
  - b. Unequivocal progression of existing non-target lesions and non-target lymph nodes. (NOTE: Unequivocal progression should not normally trump target

lesion and target lymph node status. It must be representative of overall disease status change.)

- c. See [Section 11.3.2](#) for details in regards to the requirements for PD via FDG-PET imaging.

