#### 11.4.4 Overall Objective Status

**Important: Refer to [Section 11.1](#) for a full description of the correct baseline scan to use due to the retreatment after PD during treatment in the 1st 12 weeks, as well as baseline scan to be used for crossover treatment.**

The overall objective status for an evaluation is determined by combining the patient's status on target lesions, target lymph nodes, non-target lesions, non-target lymph nodes, and new disease as defined in the following table:

Target Lesions & Target Lymph Nodes	Non-Target Lesions & Non-Target Lymph Nodes	New Sites of Disease	Overall Objective Status
CR	CR	No	CR
CR	Non-CR/Non-PD	No	PR
PR	CR Non-CR/Non-PD	No	PR
CR/PR	Not All Evaluated*	No	PR
SD	CR Non-CR/Non-PD Not All Evaluated*	No	SD
Not all Evaluated	CR Non-CR/Non-PD Not All Evaluated*	No	Not Evaluated (NE)
PD	Unequivocal PD CR Non-CR/Non-PD Not All Evaluated*	Yes or No	PD
CR/PR/SD/PD/Not all Evaluated	Unequivocal PD	Yes or No	PD
CR/PR/SD/PD/Not all Evaluated	CR Non-CR/Non-PD Not All Evaluated*	Yes	PD

\* See [Section 11.4.3.1](#)

**11.4.5 Symptomatic Deterioration:** Patients with global deterioration of health status requiring discontinuation of treatment without objective evidence of disease progression at that time, and not either related to study treatment or other medical conditions, should be reported as PD due to “symptomatic deterioration.” Every effort should be made to document the objective progression even after discontinuation of treatment due to symptomatic deterioration.

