### 12.2 Crossover

Any patient that is originally randomized to the Nivolumab alone arm (Arm 1) will have the option to cross over to the nivolumab + ipilimumab combination therapy **ONLY IF** they were removed due to disease progression. Eligibility must be evaluated as per [Section 3.4](#) and patients must be re-registered to the crossover portion of the study per [Section 4.6](#).

Once patients re-register and cross-over to the nivolumab + ipilimumab dual therapy, all cross over patients must have a scan  $\leq$  28 days of starting their new treatment as per [Section 5.0](#).

Crossover patients previously removed from Arm 1 for progression who were being followed for survival will no longer be followed by the survival schedule nor survival case report form but will proceed to the crossover treatment schedule, crossover test schedule, and crossover case report forms. Cycles/data collection will resume from the last treatment cycle patient received. Contact the data manager for assistance with RAVE data entry.

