## 13.4 Secondary Endpoints

- Evaluating adverse event rates (NCI CTCAE v4.0), within each study treatment arm. Categorical data analysis will be used to summarize adverse event rates and as a maximum severity during treatment for each patient and AE classification.
- Evaluating duration of response, clinical benefit rate (CBR), progression-free survival (PFS), and overall survival (OS), within each study treatment arm. Patients having PD within the first 12 weeks of starting treatment which is not a PD at their 4 week confirmation assessment will not be classified as having PD for time to event analyses. That is, estimates for response, CBR, and PD endpoints will not be censored at the first PD in such cases. Patients who are unable to continue treatment for a 4-week confirmation of PD occurring within the first 12 weeks of treatment will be counted as having PD at their first date of PD during the treatment period (eg, initial, crossover). In addition, disease assessment data beyond the date of crossover will not be included in the evaluation of the primary endpoint and for those patients crossing to dual agent treatment from single agent treatment. Such patients will be censored for estimating

duration of response, CBR, and PFS. Patients will be additionally censored at their most recent disease assessment prior to receiving any anti-cancer therapy after ending study treatment.

Kaplan-Meier methodology will be used to evaluate time to event endpoints: duration of response (time from first response to disease progression), PFS (time from randomization to the earliest of either disease progression or death from any cause), and OS (time from randomization to death from any cause). The CBR will be evaluated by counting up the number of patients with a response or stable disease (PR, CR, SD) and dividing by the total number of evaluable patients. Cumulative Incidence Function methodology may be used, as appropriate.

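### Section 8.1.6 labels removal for radiation as disease progression, but Section 11.4 does not count it as progression and Section 13.4 may censor the same patient, so PFS and duration-of-response handling is unsettled

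*Combined protocol and SAP*

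**What the plan says.** **The removal rule.** Section 8.1.6, under ancillary therapy, reads in full: "Patients who require radiation therapy during protocol treatment will be removed from protocol therapy due to disease progression". It asks for no scan and makes no exception by site or indication. The neighbouring surgery rule, 8.1.8, takes patients off protocol therapy after too long an interruption without calling this progression.

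**What counts as progression.** Section 11.0 sets the standard: "Response and progression as primary endpoints will be evaluated in this study using the new international criteria proposed by the revised Response Evaluation Criteria" (RECIST 1.1). For target disease, 11.4.3.2 requires a new lesion, the FDG-PET rule, or "At least a 20% increase in PBSD" over the minimum sum together with an absolute increase of at least 0.5 cm. For non-target disease, 11.4.3.3 requires a new lesion, the FDG-PET rule, or "Unequivocal progression of existing non-target lesions and non-target lymph nodes". The one route without imaging is 11.4.5, which covers "Patients with global deterioration of health status requiring discontinuation of treatment without objective evidence of disease progression at that time"; such a case "should be reported as PD due to" symptomatic deterioration.

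**How the endpoints are handled.** Section 13.4 ends PFS at disease progression or death, and duration of response at disease progression. It does not cite 11.4 or mention removals under 8.1.6. It adds: "Patients will be additionally censored at their most recent disease assessment prior to receiving any anti-cancer therapy after ending study treatment". Section 13.3 has an equivalent sentence for the primary endpoint.

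**Where the removal reason is used again.** Section 12.2 opens crossover to Arm 1 patients only if "they were removed due to disease progression". Section 3.4.2 bars re-registration of patients taken off immunotherapy for any reason other than progression. The footnotes to Section 5.0 require follow-up of both survival and disease status in patients who have not progressed, but only of survival after progression.

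**The concern.** A patient with stable or responding disease may need one painful or threatening lesion irradiated. Read through 8.1.6, this patient left treatment because of progression. Read through 11.4, the patient has not progressed. Read through 13.4, the patient is censored at the last assessment before the radiation. Two analysts working from the same protocol could code this patient differently, and each could cite a section in support. If the patient is an event, the plan also gives no event date.

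At stake are PFS and duration of response in eight small, separately reported studies, and the make-up of the exploratory crossover group in objective 2.4, which is meant to consist of patients whose disease progressed on nivolumab.

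**Working it through.** The plan states no figure on this point, so the check is mainly of the text.

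**Step 1: does a need for radiation meet any progression criterion?** No. It is not in 11.4.3.2 or 11.4.3.3. Section 11.4.5 requires global decline in health, and one symptomatic lesion need not involve that. Section 6.1.1 supports a progression with a radiology report, a pathology report where applicable, or a clinic note for symptomatic deterioration. Radiation alone has no route. Section 13.1 also rests treatment decisions on RECIST 1.1, which 8.1.6 does not follow.

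**Step 2: does Section 13 settle the coding?** No. Section 11.5 sends the reader to Section 13 for formal definitions, but 13.4 uses disease progression without pointing back to 11.4. Its censoring rule applies if radiation counts as anti-cancer therapy and is given after study treatment ends. The second condition follows naturally, because 8.1.6 ends study treatment. The first is an inference, supported by 3.3.3 and 3.4.2, which list radiation beside chemotherapy in the washout rules.

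**Step 3: crossover.** The label in 8.1.6 nearly matches the condition in 12.2 and bears on the bar in 3.4.2. Against that, 12.2 also requires Section 3.4 to be met, 3.4.1 requires radiographic or clinical progression, 4.6 has the Registration Office confirm progression, and 7.2 requires it to be documented. The remaining opening is the undefined word clinical in 3.4.1.

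**Step 4: follow-up.** Recording the removal as progression moves the patient to survival-only follow-up under Section 5.0, so a later RECIST progression date might not be collected. With 13.4 censoring, that date would not enter the main analysis. The loss matters only for an analysis that follows patients through radiation.

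**Step 5: primary endpoint.** Both readings stop counting assessments around the time of removal. Only a response still awaiting its confirmation scan could change.

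**Step 6: possible size.** The documents give no radiation rate, so everything here is illustrative.

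- *One-time step.* In a 12-patient arm (13.3.2) with no earlier censoring, one such event lowers the Kaplan-Meier curve by 1/12 = 8.3 points at that time, and two lower it by 2/12 = 16.7 points. A censored patient causes no drop at that time.
- *Effect on the curve.* Assume exponential PFS and radiation removal as an independent competing hazard. Let *f* be the share of first outcomes that are radiation removals without progression. With hazard λ = −ln(S6)/6 per month when these are censored, counting them as events gives hazard λ/(1 − f), median (1 − f) × ln 2/λ, and 6-month PFS S6^(1/(1 − f)). Example with S6 = 10% and f = 10%: λ = 2.303/6 = 0.384 and the median is 1.81 months; as events the hazard is 0.426, the median 1.63 months, and 6-month PFS 7.7%.

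The 6-month PFS values below are the historical ones in Section 1.1; the values of *f* are assumptions.

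| 6-month PFS if censored | Median if censored (months) | Median if events, f = 5 / 10 / 20% | 6-month PFS if events, f = 5 / 10 / 20% |
|---|---|---|---|
| 8% | 1.65 | 1.56 / 1.48 / 1.32 | 7.0 / 6.0 / 4.3% |
| 10% | 1.81 | 1.72 / 1.63 / 1.44 | 8.9 / 7.7 / 5.6% |
| 14% | 2.12 | 2.01 / 1.90 / 1.69 | 12.6 / 11.3 / 8.6% |

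Median PFS falls by the fraction *f*. Across the table, 6-month PFS falls by between 1.0 point (8.0 − 7.0) and 5.4 points (14.0 − 8.6).

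**The case against.** The strongest reply is that 8.1.6 governs treatment, not endpoints. It does not say that a PFS event is recorded, 11.0 gives progression to RECIST 1.1, 13.4 never uses the off-treatment reason as an event, and 6.1.1 would not support a radiation-only progression. On that reading, the patient is already censored under 13.4 and nothing conflicts. PFS and duration of response are also secondary, are not formally tested, and are not compared between arms. Some irradiated patients will have true progression.

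Most of this stands, and it rules out three stronger inferences that a reader might draw:

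- *That 8.1.6 itself generates false PFS and duration-of-response events.* It can do so only if the label is carried into endpoint coding, and no section instructs that.
- *That patients without progression will enter the crossover group.* The condition in 12.2 is necessary, not sufficient, and 3.4.1, 4.6 and 7.2 all stand in the way. Section 3.4.1 also admits clinical progression by design.
- *That PFS is biased by 8 to 17 points.* Those are single steps under an assumed one or two patients, not lasting differences. Likewise, with two or three responders any one event can set the median duration of response, whatever its cause.

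The reply does not remove the ambiguity. Section 8.1.6 states progression as the reason, without qualification, for patients who need not meet 11.4. Nothing says that the label should be ignored in the analysis, and 12.2 and 3.4.2 do act on the removal reason.

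**Conclusion.** The inconsistency is real and worth correcting, but its reach is limited. For a patient removed for radiation without progression under 11.4, the plan supports both an event and a censored observation for PFS and duration of response. The same label bears on crossover eligibility and on follow-up. The 13.4 side of the conflict assumes that radiation counts as anti-cancer therapy given after study treatment, which is the natural reading but is not written.

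The size cannot be determined from the documents; the table shows only what assumed rates would do. The primary confirmed-response count, and the response thresholds built on it, are essentially unaffected.

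**What to change.** In 13.4, state three things:

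1. Progression for PFS and duration of response is recorded only when 11.4, including 11.4.5, is met.
2. A patient removed for radiation without such progression is censored at the last assessment before radiation, under the rule already there.
3. A sensitivity analysis counts these patients as events, with the event date named in advance.

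Separately, the sponsor should reconcile the wording of 8.1.6 with 11.4, 12.2, 3.4.1 and 3.4.2, and make clear which follow-up branch of Section 5.0 applies. Changing the recorded off-treatment reason is more than a coding edit: under 3.4.2 it would affect who may cross over. This point takes no position on the removal rule or on crossover eligibility; it asks only that the passages agree.

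The analysis part costs some wording and one extra analysis, with no added procedures. The downside is slightly fewer PFS events and possibly informative censoring, since patients who need radiation may be closer to progression than those who do not. The sensitivity analysis shows how much this matters.

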#### 8.1.7 Alliance Policy Concerning the Use of Growth Factors

Blood products and growth factors should be utilized as clinically warranted and following institutional policies and recommendations. The use of growth factors should follow published guidelines of the American Society of Clinical Oncology 2006 Update of Recommendations for the Use of White Blood Cell Growth Factors: An Evidence-Based, Clinical Practice Guideline. *J Clin Oncol* 24(19): 3187-3205, 2006.

**Epoetin (EPO):** Use of epoetin in this protocol is permitted at the discretion of the treating physician.

#### **Filgrastim (G-CSF) and sargramostim (GM-CSF)**

1. Filgrastim (G-CSF)/pegfilgrastim and sargramostim (GM-CSF) treatment for patients on protocols that do not specify their use is discouraged.
2. Filgrastim/pegfilgrastim and sargramostim may not be used:
  - a. To avoid dose reductions, delays or to allow for dose escalations specified in the protocol.
  - b. For the treatment of febrile neutropenia the use of CSFs should not be routinely instituted as an adjunct to appropriate antibiotic therapy. However, the use of CSFs may be indicated in patients who have prognostic factors that are predictive of clinical deterioration such as pneumonia, hypotension, multi-organ dysfunction

(sepsis syndrome) or fungal infection, as per the ASCO guidelines. Investigators should therefore use their own discretion in using the CSFs in this setting. The use of CSF (filgrastim/pegfilgrastim or sargramostim) must be documented and reported.

- c. If filgrastim/pegfilgrastim or sargramostim are used, they must be obtained from commercial sources.

**8.1.8 Surgery:** Patients who require surgery during protocol treatment may proceed as such, unless the surgery involves resection of sarcoma. Study drug should be held for a maximum of 42 days. If the patient requires an interruption of > 42 days, then they will be removed from protocol therapy.

**8.1.9 Infusion reactions:** See [Appendix V](#) for management.

**8.1.10 Immune related toxicity:** Both ipilimumab and nivolumab can lead to a variety of immune manifestations. The following supporting care guidelines are given for specific toxicities:

- **Colitis:** Typical symptoms of immune-mediated enterocolitis are diarrhea, abdominal pain, mucus or blood in stool, with or without fever. Consider evaluation to ensure that there is not an infectious etiology. Consider treatment with anti-diarrheals or corticosteroids at the discretion of the treating physician. Evaluation by GI should be considered. Treating physicians should consider the risk of perforation with colitis and utilize anti-diarrheals with this in mind. Recommend evaluation for all patients for additional causes including C. diff, acute and self-limited infectious and foodborne illness, ischemic bowel, diverticulitis, and IBD.
- **Pneumonitis:** Patients with suspected pneumonitis should undergo full evaluation, which may include CT scan, PFTs, O2 saturation, bronchoscopy. Treatment may involve steroids (any grade pneumonitis) and possibly empiric antibiotics, at the discretion of the treating physician. Distinguishing inflammatory pneumonitis is often a diagnosis of exclusion for patients who do not respond to antibiotics and have no causal organism identified including influenza. Most patients with respiratory failure or hypoxia will be treated with steroids. Bronchoscopy may be required and analysis of lavage fluid for lymphocytic predominance may be helpful. Consider that new lung nodules may represent sarcoid like granuloma. Please consider recommending seasonal influenza killed vaccine, as per the bullet below (“vaccinations”).
- **Nephritis:** For suspected nephritis, the patient should be evaluated by nephrology and considered for renal biopsy.
- **Hepatitis:** For hepatitis, close monitoring with serial LFTs should be instituted. Continued treatment of active immune mediated hepatitis may exacerbate ongoing inflammation. Holding drug to evaluate LFT changes and early treatment are recommended. LFT changes may occur during steroid tapers from other events and may occur together with other GI events including gall bladder inflammation/pancreatitis.
- **Endocrinopathy:** At the discretion of the treating physician: consider endocrine consult, draw all appropriate labs (such as cortisol, ACTH, TSH and T4), perform any appropriate imaging (such as pituitary MRI), and supplement any deficiency. It is recommended to perform any clinically indicated laboratory evaluation of pituitary function before beginning steroid therapy or replacement therapy of any kind.
- **Gastritis:** In patients with nausea or vomiting consider evaluation for upper GI inflammation and other immune related events.

- **Rash:** Consider dermatology consult and skin biopsy, at the discretion of the treating physician. Patients with purpuric or bullous lesions must be evaluated for vasculitis, Steven-Johnson syndrome, TEN, and autoimmune bullous disease including oral lesions of bullous pemphigus/pemphigoid. Pruritus may occur with or without skin rash and should be treated symptomatically. Please be aware of the possibility that additional autoimmune events that may occur shortly after the appearance of skin rashes or pruritus and during the steroids withdrawal period.
- **Neuropathy:** Consider neurology consult for any grade 3 or 4 neuropathy, at the discretion of the treating physician.
- **Pancreatitis:** Patients may develop symptomatic and radiologic evidence of pancreatitis as well as DM and DKA. Lipase elevation may occur with other immune mediated events including colitis, hepatitis, and gall bladder inflammation.
- **Immunosuppressive agents:** Steroids are recommended as first line intervention for the immune related toxicity of these drugs. Steroids should be started prior to obtaining results of any testing, based on clinical indications for steroid initiation. Specifically: Prior to starting corticosteroids or hormone replacement for any reason, appropriate endocrine testing including cortisol, ACTH, TSH and T4 should be obtained to document baseline pituitary function which may be suppressed on treatment. Steroids should be tapered over 1 month if clinically appropriate, while monitoring for any return of toxicity. Potential second line agents are mycophenolate, cyclophosphamide, infliximab, IVIG, etc., at the discretion of the treating physician.
- **Vaccination:** Flu vaccine, pneumococcal vaccine, and any other relevant vaccines are recommended PRIOR to initiation of protocol therapy, at the discretion of the treating physician.

**8.1.11 Fatigue:** Fatigue is the most common adverse event associated with immune checkpoint therapy. Consider evaluation for associated or underlying organ involvement including pituitary disease, thyroid disease, and liver disease, or muscle inflammation

**8.1.12 Fever:** Patients may experience isolated fever during infusion reactions or up to several days after infusion. Continued fever over the course of 1-2 weeks may represent autoimmune events, or infection. Appropriate workup should be initiated, at the discretion of the treating physician.

**8.1.13 Supplementation:** Electrolyte abnormalities should be adequately corrected with appropriate supplementation upon discovery.

